Research question and objectives	This post authorization safety study (PASS) is an international, observational cohort study (registry) of pregnancy outcomes in women with multiple sclerosis (MS) exposed to LEMTRADA during pregnancy.
	Pregnancy outcomes in women exposed to LEMTRADA will be compared with available data from external comparison groups: women with MS not exposed to LEMTRADA, and women without MS.
	This is an observational study with no experimental intervention utilized. Women enrolled in the study may receive treatment and evaluations for their MS and their pregnancies as determined by their treating physicians in accordance with local standard of care. Both prospective and retrospective (exposed to LEMTRADA during pregnancy but the pregnancy outcome known at time of registry) data are collected but analyzed separately. Information of prospective pregnancies will be collected during each trimester and within 6 weeks after the end of pregnancy. For all live births, the infant's Health Care Provider (HCP) will be contacted at 1 year post-delivery to obtain follow-up on the infant's health status.
	The total duration of the study is expected to be approximately 5 years, with study recruitment expected to be 4 years.
	The main objective of this registry is to assess maternal, fetal and infant outcomes in women exposed to LEMTRADA during pregnancy. The registry will detect and record:
	Primary outcome: spontaneous abortion
	Secondary outcomes: major and minor congenital malformations, pregnancy outcome (stillbirth, elective termination, preterm birth, full-term live birth), small for gestational age at birth, any other adverse pregnancy outcomes.
	For the prospectively collected cases, these outcomes will be assessed throughout pregnancy. Infant outcomes, including effects on postnatal growth and development, will be assessed through the first year of life.
	Retrospectively collected cases of each outcome will be qualitatively described by maternal and pregnancy characteristics as well as timing of LEMTRADA exposure.
Country(-ies) of study	North America (NA), Europe (EU) and rest of the world (ROW).

Amended Clinical Trial Protocol 02
OBS13436 - Lemtrada

16-Nov-2016 Version number: 1

Author	

Marketing authorization holder(s)

Marketing authorization holder(s)	Genzyme Therapeutics, Ltd
MAH/MAH REPRESENTATIVE contact person (Qualified Person responsible for Pharmacovigilance, QPPV)	

2 LIST OF ABBREVIATIONS

AE: adverse event

BDE: Birth Defect Evaluator CI: confidence intervals CRFs: Case Report Forms

FDA: Food and Drug Administration

GD: Gestation Day

GEP: Good Epidemiology Practice

HCPs: health care providers

huCD52: human CD52

ICF: Informed Consent Form

IEC: Independent Ethics CommitteeIgG: human immunoglobulin GIRB: Institutional Review BoardMAH: Marketing Authorization Holder

MS: multiple sclerosis

PASS: post authorization safety study

SAEs: serious adverse events

3 RESPONSIBLE PARTIES

The execution of this protocol is the responsibility of the following parties:

- Marketing Authorization Holder (MAH),
- Clinical Research Organization (CRO) (MAH representative)
- National Coordinators for each country in which the study (registry) is operational,
- Scientific Advisory Committee.

3.1 MARKETING AUTHORIZATION HOLDERS

Marketing Authorization Holder oversees the activities of CRO, meets regulatory reporting responsibilities which includes the submission of the protocol, where required by national regulations, for Health Authority/Ministry of Health approval, and facilitates Competent Authority submissions.

3.2 MAH REPRESENTATIVE

The MAH Representative for this study is INC RESEARCH) (based in North Carolina, USA), a contract research organization delegated to serve as the Study (registry) Coordinating Centre. The MAH Representative is responsible for the operational conduct of the study including recruiting, training, and quality control of the National Coordinators throughout the duration of the study, facilitating data collection through the National Coordinators, ensuring adherence to local regulations including data privacy, and overseeing the work of the National Coordinators. In addition, the MAH/CRO will perform the statistical analyses, draft the study reports and other study documents.

3.3 NATIONAL COORDINATORS

Each country will have a National Coordinator (a physician appointed by the Study Coordinating Centre) responsible for the conduct of the study in his or her country. The National Coordinators' responsibilities include obtaining required approvals from Ethics Committees, facilitating the collection of study data through health care providers (HCPs), confirming the eligibility of reported cases including obtaining copy of signed Informed Consent Forms (ICF) for verification purposes, and de-identifying all Case Report Forms (CRFs) and supplemental documentation prior to sending to the Study Coordinating Centre for further processing and data entry.

3.4 SCIENTIFIC ADVISORY COMMITTEE

A Scientific Advisory Committee (SAC) oversees the scientific affairs of the study as needed, and is composed of experts in the fields such as neurology, teratology, epidemiology, maternal-fetal medicine, obstetrics and gynecology, pediatrics, etc. from various sectors (e.g., academia, private practice).

An individual or individuals of the experts with expertise in teratology/dysmorphology, will be a member (or members) of the SAC and function as the Birth Defect Evaluator(s) (BDE) to provide a detailed review of each reported case with a birth defect or with a condition that may potentially represent a birth defect and to reach a consensus on the classification /coding of each birth defect (see Section 9.4). The BDE is responsible for reviewing all birth defect cases received or updated during each reporting period. The BDE will report its findings to the SAC for review and approval.

The Scientific Advisory Committee does not contain any members from MAH or CRO. The Composition and details of functioning of Scientific Advisory Committee will be addressed in its Charter.

4 ABSTRACT

Title:

International LEMTRADA Pregnancy Exposure Cohort in Multiple Sclerosis

Rationale and background:

LEMTRADA is a recombinant humanized monoclonal antibody for intravenous infusion indicated for the treatment of patients with relapsing forms of multiple sclerosis (MS). LEMTRADA binds to CD52, a cell surface antigen present at high levels on T and B lymphocytes, and at lower levels on natural killer cells, monocytes, and macrophages. The mechanism by which LEMTRADA exerts its therapeutic effects in MS is unknown, but may involve immunomodulation through the depletion and repopulation of lymphocytes.

There are no adequate and well-controlled studies of LEMTRADA in pregnant women. It is not known whether LEMTRADA can affect reproductive capacity or cause fetal harm when administered to a pregnant woman.

Research question and objectives:

This post authorization safety study (PASS) is an international, observational cohort study (registry) of pregnancy outcomes in women with MS exposed to LEMTRADA during pregnancy.

Pregnancy outcomes in women exposed to LEMTRADA will be compared with available data from external comparison groups: women with MS not exposed to LEMTRADA, and women without MS.

The overall goal of the registry is to compare maternal, fetal and infant outcomes in women exposed to LEMTRADA with the outcomes of unexposed external comparison groups. This registry will detect and record the following outcomes:

- Primary outcome:
 - Spontaneous abortion
- Secondary outcomes:
 - Major and minor congenital malformations;
 - Pregnancy outcome: stillbirth, elective terminations, preterm birth, full-term live birth;
 - Small for gestational age at birth;
 - Any other adverse pregnancy outcomes.

These outcomes will be assessed throughout pregnancy. Infant outcomes, including effects on postnatal growth and development, will be assessed through the first year of life.

Study design:

This is an international, observational cohort registry of maternal, fetal and infant outcomes in women with MS exposed to LEMTRADA during pregnancy.

Pregnancy outcomes in women exposed to LEMTRADA will be compared with available data from external comparison groups: women with MS not exposed to LEMTRADA, and women without MS.

This is an observational study with no experimental intervention utilized. Women enrolled in the study may receive treatment and evaluations for their MS and their pregnancies as determined by their treating physicians in accordance with local standard of care. Information of prospective pregnancies on patient's safety and pregnancy outcome will be collected during each trimester and within 6 weeks after the end of pregnancy. For all live births, the infant's HCP will be contacted at 1 year post-delivery to obtain follow-up on the infant's health status. Information of retrospective pregnancies (exposed to LEMTRADA during pregnancy but pregnancy outcome is known at time of registry) will be collected similarly, except for information on the chronological interview during pregnancy.

The total duration of the study is expected to be approximately 5 years, with study recruitment expected to be 4 years.

Population:

Inclusion criteria:

- I 01. Women with MS who were or became pregnant within the period of time between the first infusion of a course of treatment with LEMTRADA to 4 months after their last infusion for that course.
- I 02. Able and willing to provide informed consent.

Exclusion criteria:

E 01. Previous enrollment in this study for a previous pregnancy.

Variables:

Rates of spontaneous abortion, major and minor congenital malformations, stillbirth, elective terminations, preterm birth, small for gestational age at birth, and any other adverse pregnancy outcomes for women exposed to LEMTRADA during pregnancy will be calculated.

These rates will be compared with corresponding rates in unexposed external comparison groups (details defined in the "Data sources" section below).

16-Nov-2016 Version number: 1

Data sources:

Exposed group:

Data of prospective pregnancies will be collected via interview during each trimester and at the pregnancy outcome interview which will occur within 6 weeks after the end of the pregnancy. Data on birth and neonatal outcomes will be collected from the women's/newborn's HCP during such pregnancy outcome interview. For all live births, the infant's HCP will be contacted at 1 year post-delivery to obtain follow-up on the infant's health status. Data will be collected on LEMTRADA exposure during pregnancy and subsequent pregnancy and fetal outcomes. Major and minor congenital malformations will be reviewed and classified by the BDE and reviewed by the SAC. This study will also collect information on maternal history including demographic information, risk factors, and medications used.

Data of retrospective pregnancies will be collected similarly except for data on the chronological interview during pregnancy as the pregnancy outcome is known at time of registry.

Comparison groups:

External comparison groups will be comprised (but not limited to) using the following sources:

- Data from the comparison groups enrolled in the North American AUBAGIO® (teriflunomide) Pregnancy Outcome Exposure Registry: an OTIS Autoimmune Disease in Pregnancy Project (Genzyme study OBS13499).
 - Cohort II (North American AUBAGIO Pregnancy Outcome Exposure Registry Cohort II) pregnant women with MS not exposed to AUBAGIO during the current pregnancy modified to also exclude women exposed to LEMTRADA
 - Cohort III (North American AUBAGIO Pregnancy Outcome Exposure Registry Cohort III) pregnant women without MS and not exposed to AUBAGIO during the current pregnancy modified to also exclude women exposed to LEMTRADA.

NOTE: Cohort I (pregnant women with MS exposed to AUBAGIO) are excluded.

- Data from the population-based European Surveillance of Congenital Anomalies (EUROCAT) database (1).
- Data from the Metropolitan Atlanta Congenital Defects Program (MACDP) (2)

Study size:

The sample size of approximately 204 women exposed to LEMTRADA during pregnancy (prospective) is expected to achieve approximately 193 women followed up to 1 year post-delivery, allowing approximately 5% of recruited women to have missing pregnancy outcome data. With this sample size and a sample size of 117 in the comparator group, at 80% power and a 1-sided two-sample test with significance level of 0.025, we will be able to detect a 2.0-fold higher relative risk for a background spontaneous abortion rate of 13.5%, which encompasses the likely risk range for spontaneous abortions amongst women in reference cohorts. In the reference cohorts of pregnancies from women with and without MS who were not exposed to LEMTRADA, the rate of spontaneous abortion is expected to be 16.6% for women without MS (3) and 11.5% - 19.5% for women with MS) (4,5,6). Retrospective pregnancies are not part of this sample size calculation and are collected additionally.

Data analysis:

Rates and 95% confidence intervals (CI) of major and minor congenital malformations, spontaneous abortion, stillbirth, elective terminations, preterm birth, small for gestational age at birth, and any other adverse pregnancy outcomes for women exposed to LEMTRADA during pregnancy will be calculated. These rates will be compared with corresponding rates in unexposed external comparison groups (details defined in Section 4, under "Data sources") by calculating a relative risk for each outcome and its 95% CI.

For retrospectively collected pregnancies, descriptive statistics on outcomes and maternal characteristics will be provided separately from prospective cases. The retrospectively collected congenital malformation cases will also be examined to determine if there is a specific pattern of malformations observed with LEMTRADA exposure.

Milestones:

- First Patient In (start of data collection): 2015
- Study progress report: in RMP update or applicable annual report
- Last Patient In: 2018
- Last Patient Out (end of collection data): 2020
- Database lock: 2021
- Final report of study results: 2021

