9.5 STUDY SIZE

9.5.1 Determination of sample size (LEMTRADA exposed)

The sample size of approximately 204 women exposed to LEMTRADA during pregnancy (prospective) is expected to achieve approximately 193 women followed up to 1 year post-delivery, allowing approximately 5% of recruited women to have missing pregnancy outcome data. With this sample size and a sample size of 117 in the comparator group, at 80% power and a 1-sided two-sample test with significance level of 0.025, we will be able to detect a 2.0-fold higher relative risk for a background spontaneous abortion rate of 13.5%, which encompasses the likely risk range for spontaneous abortions amongst women in the reference cohorts. In the reference cohorts of pregnancies from women with and without MS who were not exposed to LEMTRADA, where the rates of spontaneous abortion is expected to be 16.6% for women without MS (3) and 11.5% - 19.5% for women with MS (4,5,6). Retrospective pregnancies are not part of this sample size calculation and are collected additionally.

Table 1 shows the type of differences that may be detected comparing LEMTRADA-exposed pregnancies with various background rates for spontaneous abortion and any birth defects. For purposes of sample size calculation, a combination of general population background rates and rates published in the literature for women with MS with pregnancies unexposed to disease-modifying therapy were used.

16-Nov-2016 Version number: 1

Table 1 - Sample Size and Detectable Effect Size for Selected Endpoints

Endpoint	Population	Background Rate	Total Sample size	RR
Spontaneous abortion	General population	16.6% (3)	204 (Effective 193)	1.86
	Women with MS	11.5% (5)	204 (Effective 193)	2.12
	Women with MS	19.5% (4)	204 (Effective 193)	1.77
	Background Comparator Groups	13.5%	204 (Effective 193)	2.0
Any major birth defect General population		3% (8,9)	204 (effective 154)	4.05
	Women with MS	3% (10)	204 (effective 154)	4.05

RR: Relative Risk.

Sample size calculations were performed using EAST software version 6.2.

Assuming 5% drop out (outcome unavailable): 204*95%=193 patients will permit detection of RR=2.0 for a background rate of 13.5% with 80% power and 0.025 significance level based on 1-sided two sample Fisher's exact test (with comparator group sample size =117)

Assuming 80% live birth, 193*80%=154 live births.

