9.5.2 Sample size of external comparison groups (LEMTRADA non-exposed)

Sample size is set at 125 in comparison Cohorts II and III respectively in "AUBAGIO (teriflunomide) Pregnancy Outcome Exposure Registry: an OTIS Autoimmune Disease in Pregnancy Project" (Genzyme study OBS13499)." For the sample size calculation above, it is assumed that a sample size of 125 in the comparator group includes 4% missing data and 2% were exposed to LEMTRADA (in Cohort II), resulting in 125*96%*98% = 117 subjects.

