9.7.5 Statistical methods

Endpoints are prospectively collected rates of spontaneous abortion, major and minor congenital malformations, stillbirth, elective terminations, preterm birth, small for gestational age at birth, and any other adverse pregnancy outcomes for women exposed to LEMTRADA during pregnancy.

All the comparisons below between women exposed to LEMTRADA during pregnancy (prospectively collected) and unexposed comparison groups will be carried out separately against each comparison group.

Rates and 95% CI will be calculated. Rates will be compared between women exposed to LEMTRADA during pregnancy (prospective) and women in unexposed comparison groups by calculating the relative risk (RR) and its 95% CIs. As the majority of the events rates are anticipated to be low, when applicable, comparisons will be conducted using exact statistical methods.

A supportive analysis of (prospective) spontaneous abortion as a time-to-event endpoint will be conducted using the Kaplan-Meier method adjusting for left-truncation. If data are available, propensity score matching and covariate adjustment may be used in the Cox regression context with left-truncation to adjust for potential confounding factors, such as gestational age at enrollment, comorbidities, prior birth defects/abnormalities, exposure to other medications, etc.

For other endpoints (prospective), if data are available, propensity score matching and covariate adjustment may also be used in the logistic regression context to adjust for potential confounding factors. These approaches will reduce the influence of risk modifiers in determining the event risk ratio between Lemtrada-exposed women and non-Lemtrada-exposed women.

Qualitative descriptive statistics on maternal and pregnancy characteristics and the timing of LEMTRADA exposure will be provided for the retrospectively collected pregnancy cases.

Additional supportive analyses will be documented in the statistical analysis plan (SAP).

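### The one-sided Fisher's exact test behind the sample size gives 77% to 79% power for spontaneous abortion, slightly under the stated 80%; Boschloo's exact test reaches 80% with the same women

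*Protocol*

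**What the plan says.** Section 4 (Study size) and the text of Section 9.5.1 give the same power statement for spontaneous abortion, the primary outcome: "at 80% power and a 1-sided two-sample test with significance level of 0.025, we will be able to detect a 2.0-fold higher relative risk", at a background rate of 13.5%. Neither sentence names the test. The note under Table 1 in Section 9.5.1 does: the detection of a relative risk (RR) of 2.0 is claimed "with 80% power and 0.025 significance level based on 1-sided two sample Fisher's exact test", with 117 comparator women.

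Table 1 gives detectable RRs for three other background rates of spontaneous abortion: 1.86 at 16.6%, 2.12 at 11.5% and 1.77 at 19.5%, each with 193 effective exposed women. Section 9.5.2 derives the comparator size, "resulting in 125*96%*98% = 117 subjects".

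For the analysis, Section 9.7.5 plans rates, RRs and 95% confidence intervals against each comparison group separately. Because most event rates are expected to be low, it adds that, when applicable, "comparisons will be conducted using exact statistical methods". It does not name Fisher's test or any other.

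**The concern.** Fisher's exact test conditions on the total number of events. With discrete data it usually rejects less often than its nominal level allows, so a calculation based on it can fall short of a power figure that a normal approximation would support. The stated 80% therefore needed checking against the named test.

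The direction matters in a safety registry. A test that leaves part of its permitted error rate unused makes it more likely that a real doubling of spontaneous abortion goes undetected. Section 9.9 expects exposed pregnancies to be rare and enrolment to be difficult, so power that costs no recruitment is worth having. The low-event-rate reason for exact methods also applies only weakly to this outcome. At 13.5% and RR 2.0 the expected counts are 117 × 0.135 = 15.8 comparator events and 193 × 0.27 = 52.1 exposed events.

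**Working it through.** **Inputs, all from the protocol.**
- Exposed women: 204 × 0.95 = 193.8, used as 193 (Section 9.5.1).
- Comparator women: 125 × 0.96 × 0.98 = 117.6, used as 117 (Section 9.5.2).
- Test: one-sided Fisher's exact at 0.025 (note to Table 1).
- Background rates and RRs: the four spontaneous-abortion rows of Table 1. In the 13.5% row the exposed rate is 2.0 × 13.5% = 27.0%.

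**Method.** Let X ~ Bin(193, p₁) be exposed events and Y ~ Bin(117, p₀) comparator events, independent, with p₁ = RR × p₀. For each of the 194 × 118 possible tables, the one-sided Fisher p-value is the hypergeometric tail P(X ≥ x | X + Y = x + y). Power is the sum of P(X = x) P(Y = y) over tables with p-value ≤ 0.025. The level at a common rate p is the same sum with p₁ = p₀ = p, and the size is its maximum over p.

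**The plan's own figure.** For 27.0% v 13.5% with 193 v 117, Fisher's power is 78.1%, which is 1.9 points below 80%. A pooled-variance normal approximation gives 81.3%, so the stated figure lies between the two.

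**All four spontaneous-abortion rows, 193 v 117.** Boschloo's test uses the Fisher p-value as its statistic. Its cut-off is raised as far as possible (here to about 0.032) while the rejection probability stays within 0.025 at every common rate.

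| Background rate | RR in Table 1 | Fisher power | RR at 80% power, Fisher | Boschloo power | RR at 80% power, Boschloo |
|---|---|---|---|---|---|
| 13.5% | 2.0 | 78.1% | 2.02 | 81.6% | 1.98 |
| 16.6% | 1.86 | 78.7% | 1.87 | 81.8% | 1.84 |
| 11.5% | 2.12 | 77.3% | 2.16 | 80.7% | 2.11 |
| 19.5% | 1.77 | 79.1% | 1.78 | 82.4% | 1.75 |

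**Cause.** Compared like for like at a nominal 0.025:
- Maximum over all common rates: Fisher 0.0195, Boschloo 0.0249.
- Both rates at 13.5%: Fisher 0.0169, Boschloo 0.0222.

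**Value of the difference.** At 13.5% and RR 2.0 the chance of missing a true doubling falls from 100 − 78.1 = 21.9% to 100 − 81.6 = 18.4%. With 117 comparators, Fisher's test reaches 81.4% at 235 exposed women and 81.7% at 241. Matching Boschloo's power at 193 would therefore take about 240.

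**Not every exact test helps.** The exact unconditional test on the pooled z (score) statistic, maximised over all common rates, gives 77.1% in the 13.5% row, below Fisher. The unpooled version gives 76.9%.

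**The case against.** The strongest reply is that the gap is close to rounding. Both group sizes were truncated. At the nearest whole numbers, 194 v 118, Fisher's power is 79.6% in the 13.5% row and 79.4% in the 11.5% row, because the power of an exact test moves in a saw-tooth with sample size. An RR of 2.02 is 2.0 at the precision stated, and two other rows differ by 0.01. All of this stands, and it limits the point to a small correction. It does not remove it. At the sizes the protocol itself uses, all four rows fall short in the same direction, and the 11.5% row needs 2.16 rather than 2.12. That rate comes from the largest multiple sclerosis series quoted in Section 9.5.1 (49/425). A two-sided Fisher test at 0.05 gives 80.2% in the 13.5% row, but it is not the test named.

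A second reply is that the protocol does not bind the analysis to Fisher's test. That is correct. Fisher appears only in the sample-size note, and the choice of exact test can be left to the SAP. A reader might infer that the primary analysis is fixed to an unsuitable test, but Section 9.7.5 does not say so, and Fisher's test is valid. Nor should 0.017 be read as the test's true level in general: it applies when both rates are 13.5%, and the size is 0.0195.

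Third, selection bias, which Section 9.9 calls the primary limitation, may well outweigh 3.5 points of power. That is fair, and it bears on priority. It does not make the printed power figure right.

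**Conclusion.** The point holds as a modest correction with an efficiency gain. For the test, level and group sizes in Section 9.5.1, power is 77.3% to 79.1% across the four spontaneous-abortion rows, not 80%. The corresponding detectable RRs are 2.02, 1.87, 2.16 and 1.78, and only the 11.5% row changes materially. Boschloo's test on the same women gives 80.7% to 82.4% with size within 0.025, so every spontaneous-abortion row of Table 1 then holds.

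A reader might infer that the study is seriously underpowered or that the 80% is a gross error. The figures do not support that: the shortfall in the headline row is 1.9 points.

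The result assumes independent binomial counts, exactly 193 and 117 women, and the protocol's own background rates. It is separate from whether 13.5% is the right rate and from confounding with external comparators.

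**What to change.** In Sections 9.5.1 and 9.7.5, name Boschloo's exact unconditional test for the one-sided 0.025 comparison of spontaneous abortion. Restate the power there and in Section 4 as about 82% at a 13.5% background and RR 2.0. The four spontaneous-abortion RRs in Table 1 can then stay. Do not offer the exact unconditional pooled-z (score) test as an alternative, since it gives about 77%.

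If Fisher's test is kept, restate the power as about 78% (77% in the 11.5% row), or give the RRs detectable at 80% power as 2.02, 1.87, 2.16 and 1.78.

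Either route is a change of wording, with no extra women or data. Boschloo's test needs slightly more computation, and the 95% confidence interval for the RR may not agree exactly with the test in borderline cases. The SAP should say which of the two governs the conclusion.
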